4.12.1.2 PD Biomarkers for EIA

4.12.1.2.1 EIA Blood Biomarkers

Blood biomarkers to be assessed include measurement of acetaldehyde, acetate, and ethanol. A by-participant listing of EIA blood biomarkers will be presented in SP. A summary table of Tmax, Cmax, and AUC0-2.5h of blood biomarkers will be presented by biomarker parameter, visit, time point, EIA days, treatment and placebo in PD population. The same PK parameter analysis method described in Section 4.10 will be applied to the calculations of these biomarker parameters.

The mean (\pm SD) plasma concentration – time profiles of these biomarkers will be plotted by treatment and EIA days.

The mean (\pm SD) Cmax and AUC0-4.0h of acetaldehyde, acetate, and ethanol will be plotted with EIA days by treatment.

4.12.1.2.2 EIA Physiological Responses

Quantitative assessment of 6 symptom responses during EIAs:

6 symptom variables include flushing, headache, lightheadedness, palpitations, nausea and vomiting assessed at regular intervals during the EIAs and assessed semi-quantitatively (i.e. mild, moderate, or severe)

Descriptive statistics of 6 symptom EIA assessment (n, mean, median, Q1, Q3, minimum and maximum) for Total Scores, Highest Post Dose Score, Delta 1: Peak post-dose score for a given visit's test minus the score at the pre-alcohol administration time on that day, Delta 2: Peak post alcohol administration score on the day of the test, minus the peak post-alcohol administration score for the same participant on day -1, Delta 3: The highest score attained by that participant in Delta 1 over all 6 tests after DCR-AUD was administered will be presented by treatment, placebo, and visit.

4.12.1.2.3 Relationship of acetaldehyde Cmax and EIA symptom score by EIA days

Mean (\pm SD) and individual EIA days, Acetaldehyde Cmax (μ M) data, and EIA symptom score will be plotted on the x-axis, left y-axis, and right y axis, respectively. The acetaldehyde Cmax (μ M) and EIA symptom score profiles should be plotted with different line types and symbols and distinguishable. .

4.13 Safety Evaluation

All safety summaries and analyses will be based upon the SP. All safety and tolerability parameters (AEs, laboratory data [hematology, coagulation, clinical chemistry, routine urinalysis, complement panel, and other screen test parameters], vital signs, physical exam findings, Alcohol Consumption via Timeline Follow Back, Columbia-Suicide Severity Rating Scale, Mini-International Neuropsychiatric Interview, and ECG parameters will be evaluated as following.

4.13.1 Adverse Events

All outputs for AEs/treatment-emergent adverse events (TEAEs) will be based on the SP unless specified separately in TLF shells. Describe the AE dictionary including version that is to be used to classify the AEs.

All AE summaries should provide the number and percentages of participants reporting at least one AE and the total number of events reported.

Summaries of AEs will include the following:

- Incidence of AEs - Overview (by treatment and overall)
- Incidence of TEAEs (by treatment and overall, SOC, and PT)
- Incidence of TEAEs by maximum relationship (by treatment and overall, SOC, and PT)

- Incidence of TEAEs by maximum severity (mild/moderate/severe, by treatment and overall, SOC, and PT)

Summary tables will contain counts of participants, percentages of participants in parentheses, and the number of events where applicable. A participant who has multiple events in the same SOC and PT will be counted only once in the participant counts, but all events will be included.

All Adverse Events (AEs)

All AEs will be listed including pretreatment AEs.

Treatment-emergent Adverse Event

A TEAE will be defined as any AE that emerges during treatment (i.e., AE which started after study drug administration or pre-existed that worsened in severity after study drug administration) and those will be analyzed for the purpose of safety analysis.

TEAEs will be summarized by SOC and PT, including the number and percentage of participants experiencing events, separately.

Severity

TEAEs will be summarized by SOC, PT, and severity, including the number and percentage of participants experiencing events. If a participant reports the same TEAE more than once within that SOC and PT, the TEAE with the highest severity will be used in the corresponding severity summaries.

The summaries including severity will be reported by Common Terminology Criteria for Adverse Events (CTCAE) grade presented as below.

- Grade 1: Mild;
- Grade 2: Moderate;
- Grade 3: Severe or medically significant but not immediately life-threatening;
- Grade 4: Life-threatening consequences;
- Grade 5: Death related to AE.

participants who experience the same event multiple times will be included in the most severe category. Events with missing intensity will be considered as 'Grade 3' events for summary purposes but recorded as missing in the listings.

Relationship (Causality)

TEAEs will be summarized by SOC, PT, and causality, including the number and percentage of participants experiencing events. Relationship to study drug will be tabulated respectively. If a participant reports the same TEAE more than once within that SOC and PT, the TEAE with the worst-case relationship to study drug will be in summaries including relationship to study treatment, the following relationships will be summarized: 'Not related', 'Possibly Related', 'Probably Related' and 'Definitely Related'. Participants who experience the same event multiple times will be included in the most related category. Events with missing relationship will be considered as 'Probably Related' to the last given study drug for summary purposes but recorded as missing in the listings.

Adverse Events of Special Interest (AESI)

An Injection Site Reaction (ISR) is characterized by an intense adverse reaction (usually immunologic) developing at the site of an injection after 4 or more hours post-injection. Subcutaneous administration of the study intervention may cause a specific local reaction originating around the injection site, such as erythema, itching, discomfort, and pain, and could include more severe manifestations such as ulceration or necrosis.

Potential ISRs will be evaluated and recorded as follows:

Individual signs or symptoms at the injection site with an onset of less than 4 hours from the time of study intervention administration will be recorded as individual AEs (bruising, itching, transient erythema, swelling, etc.) and not as ISRs.

Signs or symptoms at the injection site with a time to onset of 4 or more hours post-injection will be recorded as an ISR if any of the CTCAE criteria for ISR detailed below are met. Signs or symptoms at the injection site that occur ≥ 4 hours post-injection but are not specified in Table 7 should be recorded as AEs.

- Grade 1: Tenderness with or without associated symptoms (e.g., warmth, erythema, itching).
- Grade 2: Pain, lipodystrophy; edema; phlebitis.
- Grade 3: Ulceration or necrosis; severe tissue damage; operative intervention indicated.
- Grade 4: Life-threatening consequences; urgent intervention indicated.
- Grade 5: Death .

AESI will be summarized by SOC and PT, including the number and percentage of participants experiencing events. Listing of AESI will be provided.

4.13.2 Deaths, Serious Adverse Events, and Other Significant Adverse Events

Describe the listings that are to be provided. These may include the following listings:

- A by-participant listing of all deaths that occurred during the study
- A by-participant listing of all SAEs
- A by-participant listing of all AES leading to discontinuation of study treatment
- A by-participant listing of all other significant AEs

Listings should follow the format described for AEs in Section 4.13.1 if appropriate.

4.13.3 Clinical Laboratory Evaluation

Clinical laboratory test results of hematology, biochemistry, urinalysis, urinary drug screening, coagulation and serology will be provided by participant. A list of current reference ranges of laboratory assessments is included in Section 6.3. Since laboratory ranges can be participant to changes over time the reference ranges presented in Section 6.3 might differ from the ones actually used and presented on SDTM. For analysis purposes only the ranges present on the SDTM will be used.

All TLFs will display only the standard international (SI) units after conversion by means of standard conversion factors.

Quantitative clinical laboratory variables, ie, hematology, biochemistry, and urinalysis will be summarized using descriptive statistics (n, mean, SD, minimum, maximum and median) by treatment arm and time-point. Additionally, a within-participant change will be calculated as the post-baseline measurement minus the baseline measurement and summarized in the same way.

Baseline definition will be defined in section 4.2.4.

Any quantitative laboratory parameters that are given as '<xx' or '>xx' in the database will be imputed with the absolute value of the number without the sign (e.g., <2.2 will be imputed as 2.2) for the calculation of the changes from baseline and for the descriptive statistics. In the listings, no imputations will be performed, and all data will be displayed as recorded in the database.

Each laboratory result will be classified as low (L), normal (N), or high (H) at each time point according to the laboratory supplied reference ranges. For hematology and biochemistry, shift tables will be presented showing the number and percentage of participants with shifts from baseline to each postdose time point. Tabulations will be presented by treatment arm.

Measurements obtained at Screening and EOS will not be included in the shift tables.

Measurements obtained prior to dosing in each period will be included in the tabulations for the treatment received in that specific treatment period.

Frequency tabulations of qualitative clinical laboratory variables (urinalysis) will be presented by treatment and time-point.

All laboratory data will be displayed in listings

Laboratory abnormalities that are considered clinically significant (CS) are recorded in the database as AEs. Therefore, no tabulation of laboratory values meeting any CS criteria (except liver chemistry) will be presented as all relevant information will be presented in the AE summaries.

Results of pregnancy tests (females only), serology, drugs of abuse and alcohol tests will be listed only.

4.13.4 Vital Signs,

Temperature (by skin refraction), pulse rate, respiratory rate, and blood pressure will be assessed.

Blood pressure and pulse measurements will be assessed in the seated position with a completely automated device. Heart rate will be measured using telemetry during EIAs. Manual techniques will be used only if an automated device is not available. Blood pressure and pulse measurements should be preceded by at least 5 minutes of rest for the participant in a quiet setting without distractions (e.g., television, cell phones).

Temperature will be obtained in degrees Celsius (°C), pulse rate will be counted for a full minute and recorded in beats per minute, and respirations will be counted for a full minute and recorded in breaths per minute.

Vital signs data will be listed by participant including changes from baseline. Vital signs will be summarized in tabular format to include descriptive statistics (n, mean, SD, median, minimum, maximum) for absolute values and changes from baseline will be presented by treatment, and placebo and time-point.

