- ^m Participants may be discharged from clinic following collection of the 24-hour postdose PK sample. Participants will return to clinic for collection of PK samples at 72 hours postdose on Days 4 and 32.
- ⁿ EIA will be conducted on the first day of the visit once all other assessments for that day have been completed. A total of 10 EIAs will be conducted. The timing of assessments and ethanol administration are detailed in [Table 3](#).
- ^o On dosing days, ECGs will be conducted approximately 30 minutes predose and 15-to-30 minutes postdose. If multiple assessments are due, the order of assessment should be ECG, vitals, PK, and then other assessments; with PK sample collection occurring at the nominal time. At Screening and EOS, one ECG will be performed. Screening ECGs may be repeated one time for determination of eligibility.
- ^p Blood pressure, if out of range at Screening, may be repeated one time for determination of eligibility.
- ^q Blood pressure and pulse rate to be recorded 15 (\pm 5) minutes postdose.
- ^r Height will be measured and recorded at Screening. Weight will be measured and recorded at every visit.
- ^s Sample to be collected prior to ethanol administration.
- ^t Hematology to include complete blood count with differential and RBC indices. See [Section 10.2](#) for a complete list of parameters.
- ^u See [Section 10.2](#) for a complete list of parameters.
- ^v Blood samples for complement testing to be collected predose and 2, 8, and 24 hours postdose on Day 1 and Day 57.
- ^w Blood sample for ADA testing to be drawn at same time as predose PK sample on Day 1.
- ^x Plasma samples for PK analysis to be collected predose and at 1, 2, 4, 6, 8, 24, and 72 hours postdose (exception: no 72-hour PK sample is required at Day 57). A single sample will be collected on Day 168. If multiple assessments are due, the order of testing should be ECG, vitals, PK, and then other assessments, with the PK sampling performed preferably at the nominal time point. A \pm 15-minute window will be allowed for collections at 1, 2, 4, 6, and 8 hours postdose. A \pm 30-minute window will be allowed for collection at 24 hours postdose. A \pm 60-minute window will be allowed for collection at 72 hours postdose.
- ^y Participants to record any symptoms associated with use of alcohol outside of in-clinic EIAs. Diary to be issued at time of discharge from clinic and collected and reviewed upon return to clinic.

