2.2. Benefit/Risk Assessment

The summary of potential risks provided below is based on results of the ongoing FIH study ([DCR-AUD-101](#)) and on in-depth review of literature relating to the proposed approach and insights from the nonclinical pharmacology and toxicology studies.

The antisense sequence of DCR-AUD is designed to target and reduce the expression of *ALDH2* mRNA in the liver. Potential off-target complementarities at the level of a single mismatch were completely absent from the human transcripts analyzed in in-silico studies. These findings demonstrate that DCR-AUD has a high degree of specificity for the *ALDH2* mRNA. The sequence is conserved in mouse, monkey, and human, and therefore, DCR-AUD is active in all nonclinical general toxicology species evaluated. To date, DCR-A1203 has been associated with no adverse effects in nonclinical studies.

Clinical experience with the Dicerna GalXC™ siRNA platform in more than 200 patients and HVs suggests a favorable safety profile with little-to-no evidence of systemic immune stimulation or toxicities. Mild, self-limiting injection site reactions have been reported (Dicerna data on file). In addition, in the on-going DCR-AUD-101 trial, single doses of DCR-AUD (range: 80 to 960 mg) administered to 24 participants have shown good tolerability. Specifically, no SAEs have been observed, and the vast majority of AEs in the trial have been mild in severity.

As part of the study's planned mitigation strategy, all study participants will be monitored for signs or symptoms of systemic toxicity, decline in liver or kidney function, abnormalities in hematologic parameters (including platelets and coagulation parameters), and abnormalities in vital signs, ECGs, complement activation, or other relevant safety parameters.

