9.4.2. Primary Endpoint(s)

The primary endpoints of the study are the assessment of the incidence and severity of AEs and SAEs, and the changes from baseline in vital signs, 12-lead ECG, clinical laboratory tests, and physical examination findings.

All safety analyses will be performed on the Safety Population. Adverse events will be defined as treatment-emergent AEs if they have a start date on or after the administration of study intervention during the treatment period. Frequency and percentages by treatment group will be used to summarize AEs, SAEs, AEs of special interest, and AEs by relationship.

Descriptive statistics and changes from baseline will be provided for vital signs, 12-lead ECG, clinical laboratory tests, and physical examination findings by treatment group and visit.

Laboratory parameter shifts from baseline to abnormal post-baseline values will be presented by treatment group. Mean laboratory values over time will be plotted by dose group.

By-participant listings will be provided for all the safety parameters.

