4.13.6 Physical Examination

Physical examinations will include, at a minimum, assessments of the Cardiovascular, Respiratory, Gastrointestinal, Neurological, and Skin systems. Height will also be measured and recorded at Day 1 and weight will be measured and recorded at every visit.

- Investigators should pay special attention to clinical signs related to previous serious illnesses or AEs.
- All physical examinations should include inspection of the injection site.
- Abnormal physical examination findings will be listed.

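### SAP 4.13.3 specifies no by-arm summary for coagulation or complement, although protocol 9.4.2 promises by-arm statistics for all clinical laboratory tests as part of the primary endpoint

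*SAP*

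**What the plan says.** **Protocol.** The primary endpoint includes changes from baseline in clinical laboratory tests and in physical examination findings (section 3). Section 9.4.2 promises descriptive statistics on these measures, and states: "changes from baseline will be provided for vital signs, 12-lead ECG, clinical laboratory tests, and physical examination findings by treatment group and visit". It also promises laboratory shifts from baseline by treatment group. Neither sentence excludes a panel. Table 6 (section 10.2), the table of required safety laboratory assessments, includes coagulation (INR, PT, PTT) and complement (Bb, C3a, C5a). Section 2.2 lists what will be monitored under the mitigation strategy, with hematologic abnormalities "including platelets and coagulation parameters), and abnormalities in vital signs, ECGs, complement activation" among the items. The schedule of activities states: "Blood samples for complement testing to be collected predose and 2, 8, and 24 hours postdose on Day 1 and Day 57".

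**SAP.** The opening of section 4.13 names both coagulation and the complement panel among the safety laboratory data to be evaluated in what follows. Section 4.13.3 then sets out the outputs:

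- By-participant results: "hematology, biochemistry, urinalysis, urinary drug screening, coagulation and serology will be provided by participant".
- By-arm descriptive statistics and within-participant change: "Quantitative clinical laboratory variables, ie, hematology, biochemistry, and urinalysis will be summarized using descriptive statistics".
- Shifts: "For hematology and biochemistry, shift tables will be presented".
- A catch-all: "All laboratory data will be displayed in listings".

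Section 3.2.4 names coagulation among the safety laboratory variables but not complement. Section 4.13.6 says of physical examination: "Abnormal physical examination findings will be listed". Section 4.21, on changes to the planned analysis, reads Not Applicable.

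**The concern.** Two panels that belong to the primary endpoint drop out between the protocol's analysis section and the SAP's output list. A programmer working from SAP 4.13.3 would produce no active-versus-placebo table for INR, PT, PTT, Bb, C3a or C5a.

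Complement matters most here. It is sampled intensively around the first and third doses, and the natural questions are whether values rise after dosing, whether they rise more on DCR-AUD than on placebo, and whether the response at Day 57 differs from that at Day 1. A moderate rise shared by most treated participants, with no single value judged clinically significant, is the pattern that a by-arm summary shows and a listing hides. The documents set no significance threshold for complement, so escalation to an adverse event depends on individual judgement.

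**Working it through.** The plan states no figure to reproduce: protocol 9.1 and 9.2 plan no inference and no formal sample size. The check is a comparison of text plus a count.

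**Step 1. Outputs specified in SAP 4.13.3, by panel.**

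| Panel | By-arm descriptive and change | By-arm shift table | Listing |
|---|---|---|---|
| Hematology | Yes | Yes | Yes |
| Biochemistry | Yes | Yes | Yes |
| Urinalysis | Yes (with frequencies for qualitative items) | No | Yes |
| Coagulation | Not specified | Not specified | Yes, by name |
| Complement | Not specified | Not specified | Only through the catch-all |

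So 0 of the 2 panels in question have a by-arm output specified.

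**Step 2. Can coagulation be read into hematology?** No. The first sentence of 4.13.3 names the two separately, and so does Table 6 of the protocol.

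**Step 3. Does another section supply the summary?** The opening of SAP 4.13 points forward to the subsections, and none of them returns to either panel. SAP section 1 says that the document describes all planned analyses for the study report.

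**Step 4. How many complement results are affected?** Inputs: 4 time points (predose, 2, 8 and 24 h) on 2 dosing days, 3 analytes, and 16 participants (12 active, 4 placebo), with full attendance assumed.

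- Samples per participant: 4 × 2 = 8.
- Samples in all: 8 × 16 = 128.
- Results: 128 × 3 = 384, of which 12 × 8 × 3 = 288 are active and 4 × 8 × 3 = 96 are placebo.

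This counts data without a planned summary. It does not measure a safety effect.

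**Step 5. Would the tables be blanked by the small-n rule?** SAP 4.2.6 shows only n, minimum and maximum when n is below 3. With 4 on placebo, that needs at least 2 missing values at a time point (4 − 2 = 2 < 3). With complete or nearly complete data, the tables would be populated.

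**Step 6. Which baseline would apply to complement?** SAP 4.2.4 takes the last non-missing measurement before a dose, in the singular, in a study with three doses. Read as the first dose, the Day 57 samples are compared with a value from 57 − 1 = 56 days (8 weeks) earlier. Read as the dose preceding the measurement, they are compared with the Day 57 predose sample. The text does not settle which.

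**Step 7. Physical examination.** Protocol 9.4.2 includes it in the by-group, by-visit summary. SAP 4.13.6 provides a listing of abnormal findings and nothing else.

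**The case against.** The strongest reply is that this is an incomplete list and not a decision to restrict. SAP 4.13.3 has an explicit list-only sentence, covering pregnancy tests, serology, drugs of abuse and alcohol, and neither panel is on it. SAP 4.13.1 mentions table shells, which are not among the documents and might contain these tables. That probably explains the gap, but it does not close it: the SAP itself assigns the panels no by-arm output. A reader might infer that the SAP deliberately confines them to listings. The text supports only that nothing more is specified.

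A second reply is that clinically significant laboratory abnormalities are recorded as adverse events (protocol 8.2.6, SAP 4.13.3), which are tabulated by treatment. This stands, so it would be wrong to say that no by-arm information on these panels survives.

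Other tempting readings go further than the documents:

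- **That coagulation and complement are named risks of the drug.** Protocol 2.2 names them as monitored parameters. The risk table in 2.2.2 has no row for either.
- **That complement is the trial's only check on immune stimulation.** The plan also includes a differential white count, and treats injection site reactions, described as usually immunologic, as events of special interest.
- **That Day 57 will be compared with a value 8 weeks old.** That is one reading of an ambiguous definition. SAP 4.13.3 also speaks of measurements taken before dosing in each period, which leans towards a dose-specific view.
- **That coagulation is drawn at every visit.** As extracted, the schedules show four marks in protocol Table 1 and one in Table 2, fewer than the study visits.
- **That protocol 9.4.2 requires a table of new abnormal physical findings.** It promises descriptive statistics and changes by group and visit. It prescribes no such format.

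Finally, with 4 placebo participants and no inference planned, by-arm tables will be imprecise. That limits what they can show, but the protocol promised descriptive tables on the same sample size.

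**Conclusion.** The point holds as a conflict between documents. Protocol 9.4.2 promises by-arm statistics, changes and shifts for clinical laboratory tests without exception. SAP 4.13.3 specifies them for a closed list that leaves out coagulation and complement, and SAP 4.21 declares no departure. What is lost is the group-level pattern in six analytes within the primary endpoint, not the individual values and not the clinically significant cases. The complement reference is unclear and should be stated, but it is not shown to be wrong. The physical examination mismatch is real and separate.

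The conclusion assumes that the unseen table shells follow the SAP text. If they already include both panels, the correction is to the wording of the SAP only. This is a low-cost correction that should be made. It does not undermine the design.

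**What to change.** 1. In SAP 4.13.3, extend the by-arm descriptive and change-from-baseline summaries to coagulation and the complement panel.
2. Add coagulation to the shift tables. If complement is left out of them, for example because the laboratory supplies no reference range, say so in 4.21, since the protocol's shift promise excludes no panel.
3. For Bb, C3a and C5a, state the reference explicitly. Present absolute values, and change from the same-day predose sample at 2, 8 and 24 h, by arm, for Day 1 and Day 57.
4. Add complement to the safety variables in SAP 3.2.4.
5. Summarise physical examination findings by arm and visit, in a format of the sponsor's choice, or record the departure from protocol 9.4.2 in SAP 4.21.

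Because the SAP is already final, the change goes into a revision or the modification form that SAP section 1 provides for. The cost is a few tables from data already collected, with no new procedures or samples.
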